4.2.2 Evaluations (Treatment Day 1)

Subjects will return to the clinical site for screening if it was not completed previously, and the following evaluations will be performed:

1. Confirmation of eligibility.
2. Medical history to assess any changes since screening (as described in [Section 4.2.1](#)).
3. Review and recording of any concomitant medications and non-pharmacologic treatments or procedures in the last 14 Days prior to enrollment and since the last study visit.
4. Vital signs (heart rate and temperature).
5. Limited physical examination.
6. Dermatologic exam (as described in [Section 4.2.1](#)).
7. CDLQI assessment.
8. LSR assessment.

9. Urine pregnancy test for females of child bearing potential, defined as capable of menstruating, to determine protocol eligibility.
10. Photographs taken before application of the Study drug (at selected sites only).
11. Application of Study drug.
12. Review and record any AEs and concomitant medications.
13. Completion of PERIT assessment by parent or guardian approximately 24 hours following application of the Study drug.
14. Depending on age of subject, subject or parent/guardian will wash off the Study drug 24 hours post application of Study drug or when convenient after the 24 hour time point is reached provided there are no adverse reactions. Patients/guardians may gently remove the Study drug from lesions without the use of a washcloth in problematic areas prior to the expected 24 hours if the lesions have already blistered or if the patient is experiencing unmanageable pain. Study drug should not be removed from the additional lesions, where possible, until the expected blistering occurs or the 24 hour time point is reached, whichever comes first.
15. A follow-up phone call from the investigator or a designated member of the clinical research team will be conducted the following day after each treatment to allow parents/guardians to ask questions and report any concerns, confirm removal of Study drug, and review the completion of the PERIT assessment.

4.2.3 Evaluations: (Treatments Day 21, 42 and 63):

1. Review and recording of any concomitant medications and non-pharmacologic treatments/procedures since previous visit.
2. Review and recording of any AEs (before and after Study drug application).
3. Vital signs (heart rate and temperature) before Study drug application.
4. Dermatologic exam (as described in [Section 4.2.1](#)) with counting of molluscum lesions.
5. CDLQI assessment.

6. LSR assessment.
7. Safety Monitoring Questionnaire.
8. Urine pregnancy test for females of child bearing potential to confirm continued protocol eligibility before application of study drug.
9. Photographs taken before application of the Study drug.
10. Administration of study drug to all lesions including those lesions that may be newly developed. If any new lesions are not treatable, this will be documented.
11. Completion of PERIT assessment by parent or guardian approximately 24 hours following application of the Study drug.
12. Depending on age of subject, subject or parent/guardian will wash off the Study drug 16-24 hours post application of Study drug. Patients/guardians may gently remove the Study drug from lesions without the use of a washcloth in problematic areas prior to the expected 16-24 hours if the lesions have already blistered or if the patient is experiencing unmanageable pain. Study drug should not be removed from the additional lesions, where possible, until the expected blistering occurs or the 16-24 hour time point is reached, whichever comes first. If possible patients/guardians should target Study drug removal at 24 hours.
13. A follow-up phone call from the investigator or a designated member of the clinical research team will be conducted the following day after each treatment to allow parents/guardians to ask questions and report any concerns, confirm removal of Study drug, and review the completion of the PERIT assessment. Photos will be text or e-mailed by the parent/guardian to the research team for review during the 24-hour phone call.

4.2.4 Evaluation Period / End of Study (~Day 84 or earlier if patient is completely clear of molluscum):

Subjects will return to the clinical site for:

1. Review and recording of any concomitant medications and non-pharmacologic treatments/procedures since previous visit.
2. Review and recording of any AEs.

3. Vital signs (heart rate and temperature) obtained at the beginning of visit.
4. Limited physical examination.
5. Dermatologic exam (as described in [Section 4.2.1](#)) and counts of treated and untreated lesions.
6. LSR, CDLQI and Safety Monitoring assessments.
7. Urine pregnancy test for females of childbearing potential.
8. Photographs

5.0 PROCEDURES FOR HANDLING ADVERSE EVENTS AND SERIOUS ADVERSE EVENTS**5.1 DEFINITION OF AN ADVERSE EVENT**

The following definition of *adverse event* (AE) will be used for this study:

Adverse event means any untoward medical occurrence associated with the use of a drug in humans, whether or not considered drug related.

An AE can be any unfavorable and unintended sign, symptom, or disease (new or exacerbated) temporally associated with the use of the investigational product, regardless of whether it is considered to be related to the investigational product.

The following are examples of AEs:

- Exacerbation of a chronic or intermittent preexisting condition, including an increase in frequency or intensity of the condition
- New conditions detected or diagnosed after investigational product administration, even if they were present before the start of the study
- Signs, symptoms, or the clinical sequelae of a suspected interaction with another medical product

Examples of AEs do not include the following:

- Medical procedures (The medical condition that led to the procedure as the AE should be reported.)
- Situations that are unwanted by the subject but in which an untoward medical occurrence did not occur, for example social inconvenience after admission to a hospital
- Anticipated day-to-day fluctuations of a preexisting disease or condition (present or detected before enrollment) that does not worsen overall

- Expected progression of the disease being studied, including signs or symptoms of the disease, unless progression is more severe than expected for the subject's condition

AEs may include pretreatment or post treatment events that occur as a result of protocol-mandated procedures (e.g., invasive procedures, modification of the subject's previous therapeutic regimen). AEs should be captured even if they occur during periods without drug treatment or post treatment periods. AE collection begins once the patient has signed informed consent and will continue until the EOS visit has been completed.

The investigator is responsible for performing periodic and special assessments for AEs. The investigator and study personnel will note all AEs mentioned by the subject starting from the day the informed consent is signed and during administration of the investigational product, until the end of study visit (Day 84). All clinical complaints volunteered by or elicited from the subject or parent/guardian during the study will be recorded on the appropriate page of the eCRF for the study period indicated. The subject and parent/guardian will receive appropriate treatment and medical supervision for any AE that occurs.

All AEs judged to be clinically significant will be followed until the EOS visit or until they have stabilized. All AEs will be summarized in the annual report or more frequently if requested by the regulatory agency. SAEs require special reporting in addition to documentation in the eCRF as described in [Section 5.3](#).

5.2 DEFINITION OF A SERIOUS ADVERSE EVENT

In this study, a *serious adverse event* is defined as an AE that meets any of the following criteria:

- Results in death
- Is life-threatening

The term *life-threatening* in the definition of an SAE refers to an event in which the subject was at risk of death at the time of the event. The term *life-threatening* does not refer to an event that hypothetically might have caused death if it were more severe.

- Requires hospitalization or a prolongation of an existing hospitalization

In general, hospitalization signifies that the subject has been detained at the hospital or emergency ward for observation or treatment that would not have been appropriate in the physician's office or out-patient setting. Complications that occur during hospitalization are AEs, but not necessarily SAEs. An occurrence or complication that prolongs hospitalization is an SAE. When there is doubt as to whether hospitalization occurred or was necessary, the AE should be considered an SAE. Hospitalization for elective treatments of a preexisting condition that did not worsen from its original baseline level is not considered an SAE.

- A persistent or significant incapacity or substantial disruption of the ability to conduct normal life functions

This definition is not intended to include AEs of relatively minor medical significance such as uncomplicated headache, nausea, vomiting, diarrhea, influenza and accidental trauma (e.g., sprained ankle) that may interfere or prevent everyday life functions but do not constitute a substantial disruption.

- Other important medical event

Medical or scientific judgment should be exercised when deciding whether reporting is appropriate for other important medical events that may not result in death, be

life-threatening, or require hospitalization but still may jeopardize the subject or may require medical intervention to prevent one of the outcomes listed in this definition. These events should also be considered serious. Examples of such events are intensive treatment in an emergency room or at home for allergic bronchospasm, blood dyscrasias, or convulsions that do not result in hospitalization.

An SAE requires additional detailed reports and follow-up. The content of these detailed reports must address the investigator's estimate of causality. The medical monitor will review the SAE to determine if it is an expected SAE (i.e., whether or not the SAE is identified in nature, severity, and frequency in the VP-102 Investigator's Brochure).

5.3

RECORDING ADVERSE EVENTS AND SERIOUS ADVERSE EVENTS

When an AE or SAE occurs, the investigator is responsible for reviewing all documentation (e.g., hospital progress notes, laboratory, and diagnostic reports) relative to the event(s). The investigator will record all relevant information about any AE (including SAEs) on the AE page of the CRF. It is not acceptable for the investigator to send photocopies of the subject's medical records in lieu of the properly completed AE or SAE pages of the CRF. These documents should not be sent unless they are specifically requested by the designated Medical Monitor. If this request occurs, all subject identifiers and protected health information should be blinded on the copies of the medical records before submission to the Sponsor and to the appropriate authorities.

The investigator will also attempt to report a diagnosis, instead of signs, symptoms, or other clinical information, for the AE. The diagnosis, not the individual signs and symptoms, should be documented on the appropriate page of the CRF as the AE or SAE. In addition, SAEs need to be reported in the SAE report. AEs being processed as SAEs will also require additional documentation.

5.4 ASSESSMENT OF INTENSITY

The investigator will assess the intensity for each AE and SAE reported during the study. The assessment will be based on the investigator's clinical judgment.

The classifications in [Table 1](#) should be used in assigning intensity of each AE recorded in the eCRF.

Table 1. Classification of AEs by Intensity^a

Intensity	Definition
Mild AE (Grade 1)	An event that is easily tolerated by the subject, causing minimal discomfort and not interfering with everyday activities
Moderate AE (Grade 2)	An event that is sufficiently discomforting to the extent of interfering with normal everyday activities
Severe AE (Grade 3)	An event that prevents the subject from performing normal everyday activities
Life-threatening or disabling AE (Grade 4)	An event that, at the time of occurrence, put the subject at risk of death or resulted in a persistent or significant disability or incapacity
Death related to AE (Grade 5)	An event that resulted in death

AE: adverse event.

a From Common Terminology Criteria for Adverse Events (CTCAE), Version 4.0.

Any AE that changes in intensity or grade during its course will be recorded in the eCRF at the highest level experienced by the subject.

An AE that is assessed as severe should not be confused with an SAE. Severity is a category used for rating the intensity of an AE (such as mild, moderate, or severe myocardial infarction). However, the event itself may be of relatively minor medical significance, such as a severe headache. Both AEs and SAEs can be assessed as severe. An AE is considered serious when it meets one of the predefined outcomes described in [Section 5.2](#).

5.5 ASSESSMENT OF CAUSALITY

The investigator must estimate the relationship between the investigational product and the occurrence of each AE or SAE by using his or her best clinical judgment. Elements to consider for this estimate include the history of the underlying disease, concomitant therapy, other risk factors, and the temporal relationship of the event to the

investigational product. The investigator will also consult the Investigator's Brochure or product label for marketed products in estimating the relationship.

Because of reporting timelines, the investigator might have minimal information to include in the initial SAE report. However, the investigator must always make an assessment of causality for every SAE before the transmission of the SAE report. The investigator may change his or her opinion of the causality in light of follow-up information, with subsequent amendment of the SAE report. Causality assessment is one of the criteria used to determine regulatory reporting requirements and should not be left blank in the SAE report. The same applies to AEs that are to be processed as SAEs. Some definitions to use in the assessment are provided in [Table 2](#).

Table 2. Assessment of Causality of AEs

Term	Definition
Definitely related	The AE is clearly related to the investigational agent(s) or research intervention: the AE has a temporal relationship to the administration of the investigational agent(s) or research intervention and follows a known pattern of response, and no alternative cause is present.
Possibly related	The AE may be related to the investigational agent(s) or intervention: the AE has a temporal relationship to the administration of the investigational agent(s) or research intervention and follows a suspected pattern of response, but an alternative cause is present.
Probably related	The AE is likely related to the investigational agent(s) or intervention: the AE has a temporal relationship to the administration of the investigational agent(s) or research intervention and follows a known or suspected pattern of response, but an alternative cause may be present.
Unrelated (or not related)	The AE is clearly not related to the investigational agent(s) or intervention: the AE has no temporal relationship to the administration of the investigational agent(s) or research intervention, and follows no known or suspected pattern of response, and an alternative cause is present.

AE: adverse event.

5.6

EXPECTEDNESS OF SERIOUS ADVERSE EVENTS

An expected AE is one that is consistent with the known risk information described in the product label (if applicable) or the current Investigator's Brochure. The expectedness of an SAE will be assessed by the medical monitor or sponsor on receipt of the initial SAE report.

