2.3.1 Safety

The following safety parameters will be assessed:

- Subjects will be monitored for signs and symptoms of AEs throughout the study. All AEs will be reported on the case report form, including seriousness, severity, action taken, and relationship to the Study drug. If AEs should occur, the first concern will be the safety of the subject.
- Limited physical examinations will be performed by a qualified medical practitioner, at screening and at EOS. Height and weight will be recorded at screening, and weight will be recorded at EOS. Unscheduled physical examinations will be performed when clinically warranted (e.g., if a subject reports symptom requiring further evaluation).
- Vital signs (e.g., heart rate and temperature) will be obtained at screening and at all subsequent visits prior to treatment. A final assessment of vital signs will be obtained at the EOS visit.
- If the subject discontinues the study prematurely (after the first treatment) due to clearance of lesions, or for any reason, attempts will be made to encourage the subject/parent/guardian to complete the EOS assessments.
- Assessment of local skin reactions (LSR) will be performed by the investigator or trained member of the research team at each treatment visit and the EOS visit. LSRs are not considered AEs and are part of the normal and necessary response to treatment. The following clinical responses will be recorded: erythema (including associated swelling), flaking/scaling, dryness and scabbing/crusting during resolution). A Skin Quality Assessment will also be performed as part of the LSR and will evaluate pigmentation changes (hyperpigmentation or hypopigmentation) and degree of scarring, if applicable.
- Patient Evaluation of Response to Treatment (PERIT)
- Safety Monitoring Questionnaire

- Households where siblings or friends are diagnosed with molluscum should make every effort to avoid close contact with those individuals to prevent development of new lesions, recurrence, or spread of the disease. Sharing of personal items such as towels, clothes, utensils or toys is strongly discouraged.

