11.2. Adverse Events

Adverse events summaries will only consider Treatment Emergent Adverse Events (TEAEs). TEAEs are defined as those adverse events that occurred after dosing and those existing adverse events that worsened during the study. If it cannot be determined whether the adverse event is treatment emergent due to an incomplete (partial) onset date, the adverse event will be considered to be treatment emergent. Verbatim terms entered into the clinical database via the EDC system will be mapped to preferred terms and system organ classes using the most current version of Medical Dictionary for Regulatory Activities (MedDRA) available.

Each adverse event summary will be displayed by treatment group. Summaries that are displayed by system organ class and preferred terms will be ordered by descending order of incidence of system organ class and preferred term within each system organ class. Summaries of the following types will be presented:

- Overall summary of the TEAEs which contain an overview of each item below.
- Subject count and incidence rate of TEAEs by MedDRA system organ class and preferred term.
- Subject count and incidence rate of TEAEs by MedDRA system organ class, preferred term and highest severity. At each level of subject summarization, a subject is classified according to the highest severity if the subject reported one or more events.
- Subject count and incidence rate of TEAEs by MedDRA system organ class, preferred term and closest relationship to study drug (Related/Not Related). Related AEs are those reported as “Definitely”, “Probable” or “Possibly”. At each level of subject summarization, a subject is classified according to the

closest relationship if the subject reported one or more events. Adverse events with missing relationship will be considered related for this summary.

- Subject count and incidence rate of Serious TEAEs by MedDRA system organ class and preferred term.
- Subject count and incidence rate of TEAEs leading to study discontinuation by MedDRA system organ class and preferred term.

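### Protocol Table 2 rates causality against the drug or a research intervention, so a blood-draw event can be tabulated as related to study drug, in the Exposure group only

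*Protocol*

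**What the plan says.** **What is to be rated.** The lead-in to Protocol Section 5.5 is explicit: "The investigator must estimate the relationship between the investigational product and the occurrence of each AE or SAE". Protocol Section 2.3.1 agrees: "All AEs will be reported on the case report form, including seriousness, severity, action taken, and relationship to the Study drug". The synopsis (Safety) and Section 7.2.5 also speak of relationship to Study drug.

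**How the levels are defined.** Table 2 is introduced with the words "Some definitions to use in the assessment are provided in" the table. Its Definitely related row applies where "the AE has a temporal relationship to the administration of the investigational agent(s) or research intervention and follows a known pattern of response" and there is no alternative cause. The Possibly, Probably and Unrelated rows carry the same double target. Unrelated also requires that there be no temporal relationship to the administration of either the agent or the intervention.

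**What counts as an adverse event.** Protocol Section 5.1: "AEs may include pretreatment or post treatment events that occur as a result of protocol-mandated procedures", with invasive procedures as an example.

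**What is tabulated.** SAP Section 11.2 summarises treatment-emergent events by "system organ class, preferred term and closest relationship to study drug (Related/Not Related"). Definitely, Probable and Possibly are pooled as related, and a missing rating is also counted as related.

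**Who has blood drawn.** Under Protocol Section 7.2.3, only the Exposure group: once before the first treatment and at 2, 6 and 24 hours after it. SAP Section 5 shows every summary table by Exposure and Standard group, with a total.

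Neither document describes a separate rating, or a separate table line, for events caused by a study procedure.

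**The concern.** One section of the protocol gives two attribution targets, and the SAP table has room for only one. An investigator who follows the lead-in rates the drug. One who applies Table 2 literally rates the drug or the procedure. The code that reaches the database does not show which was done, and the SAP labels the result as relationship to study drug.

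The error can run in only one direction and in only one group, because the Standard group has no draws. A bruise or faint in the hours after dosing could appear as a drug-related row in the very group studied for systemic exposure, and a reader of the table could take it for a systemic effect. With up to five sites, the same event could also be coded differently from site to site. Section 5.5 adds that causality is one input to regulatory reporting, so the ambiguity is not confined to a summary table.

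**Working it through.** The documents state no figure on this point, so there is none to reproduce. The check follows one event through the text and then sizes it.

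**Step 1. A bruise from the 6-hour draw.**

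| Text applied | Result |
|---|---|
| Protocol 5.1 | It is an adverse event, since it comes from a protocol-mandated invasive procedure |
| Protocol 5.5 lead-in | The product did not cause it, so it is not related |
| Table 2 read literally | The draw is a research intervention, the timing fits, the pattern is known and no other cause is present: Definitely related. Unrelated is not available |
| SAP 11.2 | Onset is after dosing, so it is treatment-emergent; Definitely maps to related to study drug |

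The second and third rows contradict each other, and the fourth takes whichever code was entered.

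**Step 2. Which draws matter.** There are 4 draws, 3 of them after dosing. Under SAP 11.2 an event that starts at the pre-application draw is not treatment-emergent unless it worsens or its onset date is too incomplete to tell.

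**Step 3. Size per affected child.** The target is 16 children completing all draws (Protocol 7.2.2). Up to 8 further subjects may be replacements. If all 8 were in the Exposure group (assumption), it would hold 24, because SAP Section 6 keeps replaced children in the Safety population.

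- 1/16 = 6.25 percentage points (exact 95% interval 0.2 to 30.2)
- 1/24 = 4.2 percentage points (0.1 to 21.1)
- Standard group: no draws, so 0

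These increments apply to a row in which the child is not already counted as related.

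**Step 4. Expected number of affected children.** The documents give no event rate per draw, so a range r is assumed, with three separate post-dose draws treated as independent: expected number = n × (1 − (1 − r)^3). For example, r = 10% and n = 16 gives 16 × (1 − 0.729) = 4.3.

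| Assumed r per draw | n = 16 | n = 24 |
|---|---|---|
| 1% | 0.5 | 0.7 |
| 2% | 0.9 | 1.4 |
| 5% | 2.3 | 3.4 |
| 10% | 4.3 | 6.5 |

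The n = 24 column is an upper bound: a child is replaced only after missing at least one draw, so not all 24 would have three post-dose draws.

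**Step 5. Would deleting the phrase be enough?** No. All three post-dose draws fall 2 to 24 hours after application. With Table 2 confined to the drug, a draw bruise still has a temporal relationship to the drug. It would therefore still fail Unrelated, which requires that there be none. That row has to be reworded as well.

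**The case against.** The strongest reply is that the target is stated correctly in several places: the Section 5.5 lead-in, which says the investigator must rate the product; Section 2.3.1 on the case report form; the synopsis; and Section 7.2.5. Table 2 only offers definitions to help. Research intervention is undefined, and since Table 2 speaks of its administration, it may simply be a generic name for the study treatment. This stands to the extent that misattribution is possible and not automatic. It does not remove the conflict. Table 2 supplies the definitions behind the codes that the SAP uses. Reading intervention as the treatment also leaves the word *or* with nothing to add, because the agent is already named, while Section 5.1 expressly brings procedures within scope.

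A second reply is that local skin reactions will swamp any effect. SAP Sections 3 and 11.3 record blistering, pain, pruritus and erythema as adverse events, and one retrospective series of 300 children cited in Protocol Section 1.2.2 reports blistering in 92%. A child is counted once at each summary level, so most are probably already related overall. This stands, and it confines the effect to individual preferred-term and system organ class rows.

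Third, the groups are split by lesion count, not randomised, and SAP Section 9.6 plans no formal comparisons. That also stands; the problem is a mislabelled row, not a biased test.

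**Conclusion.** Table 2 contradicts its own section and the SAP table it feeds. A post-dose draw event coded by Table 2 as written can be reported as a drug-related treatment-emergent event, in the Exposure group only. The firm figure is up to 6.25 points per affected child in a given row at n = 16, or 4.2 at n = 24. The expected count of about 0.5 to 4.3 of 16 children rests wholly on the assumed 1% to 10% per draw.

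A reader might infer that every draw event will become drug-related, or that the Exposure group's overall related rate will be inflated by many points and show a false excess of systemic toxicity. The documents do not support that. The lead-in points the other way, no draw-event rate is given, and local skin reactions already count as adverse events. The primary endpoint is decided by plasma concentration (SAP Section 8), not by causality ratings. Nor can it be said that no procedure field exists: the case report form was not available, and the documents merely do not describe one.

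The defect is modest, but it differs by group and is cheap to remove, so it should be corrected.

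**What to change.** 1. **Protocol Table 2.** Align it with the Section 5.5 lead-in by removing *or research intervention* and *or intervention* from every row. Reword Unrelated so that timing after dosing does not by itself rule it out when a clear non-drug cause, such as the blood draw, is present.
2. **Adverse event page.** Record relatedness to a study procedure as a separate item, or confirm that the form already has one.
3. **SAP Section 11.2.** State that only the Study-drug rating feeds the Related/Not Related table, and show procedure-related treatment-emergent events on their own line.

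The cost is table wording, one item on the adverse event page, one SAP line, and a re-query of any Exposure-group events already coded, which involves at most about 24 children.
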